13.0 Withdrawal of Subjects

13.1 Describe anticipated circumstances under which subjects will be withdrawn from the research without their consent.

Subjects will be withdrawn from the research without their consent if they are unable to complete their responsibilities listed on the consent form or if they falsify responses.

13.2 Describe any procedures for orderly termination.

The participants that require early termination from the study will receive a telephone call alerting them to the termination and thanking them for their participation. If participants are not available via telephone, a letter notifying them of their termination will be mailed to their home address.

13.3 Describe procedures that will be followed when subjects withdraw from the research, including partial withdrawal from procedures with continued data collection.

Response: It is conceivable that some participants may decide not to fully participate, for example, not wear the light therapy (i.e. Re-Timers), but complete survey and actigraph data. Their data is still valuable. Data collection would continue and participants would receive appropriate compensation.

14.0 Risks to Subjects

14.1 List the reasonably foreseeable risks, discomforts, hazards, or inconveniences to the subjects related to the subjects' participation in the research. Include as may be useful for the IRB's consideration, a description of the probability, magnitude, duration, and reversibility of the risks. Consider physical, psychological, social, legal, and economic risks.

The known risks associated with this study include the possibility that participants may become upset thinking about some of the questions or topics in this study. If this occurs, the participant should notify the research assistant and will then be provided with an appropriate referral for assistance. The skin on the participant's wrist may become irritated by wearing the actigraph. If this occurs, the participant will be advised to remove the actigraph, apply a thin layer of Eurcerin lotion to the affected area and wear the actigraph on the opposite wrist.

14.2 If applicable, indicate which procedures may have risks to the subjects that are currently unforeseeable.

Response: N/A

14.3 If applicable, indicate which procedures may have risks to an embryo or fetus should the subject be or become pregnant.

Response: N/A

14.4 If applicable, describe risks to others who are not subjects.

Response: N/A

15.0 Potential Benefits to Subjects

15.1 Describe the potential benefits that individual subjects may experience from taking part in the research. Include as may be useful for the IRB's consideration, the probability, magnitude, and duration of the potential benefits.

Response: Preliminary testing of the efficacy of light therapy has demonstrated an improvement in sleep continuity disturbances, daytime

functioning and quality of life in a variety of cancer survivors. Participants may benefit with a better sleep quality and overall quality of life. Furthermore, this light therapy device (i.e. Re-Timer) may be a more energy-efficient (through the use of LEDs) and convenient (portable method), compared to traditional light boxes.

15.2 Indicate if there is no direct benefit. Do not include benefits to society or others.

Response: Some participants may not achieve any benefit from this therapy.

16.0 Vulnerable Populations

16.1 If the research involves individuals who are vulnerable to coercion or undue influence, describe additional safeguards included to protect their rights and welfare.

- *If the research involves pregnant women, review “CHECKLIST: Pregnant Women (HRP-412)” to ensure that you have provided sufficient information.*
- *If the research involves neonates of uncertain viability or non-viable neonates, review “CHECKLIST: Neonates (HRP-413)” or “HRP-414 – CHECKLIST: Neonates of Uncertain Viability (HRP-414)” to ensure that you have provided sufficient information.*
- *If the research involves prisoners, review “CHECKLIST: Prisoners (HRP-415)” to ensure that you have provided sufficient information.*
- *If the research involves persons who have not attained the legal age for consent to treatments or procedures involved in the research (“children”), review the “CHECKLIST: Children (HRP-416)” to ensure that you have provided sufficient information.*
- *If the research involves cognitively impaired adults, review “CHECKLIST: Cognitively Impaired Adults (HRP-417)” to ensure that you have provided sufficient information.*
- *Consider if other specifically targeted populations such as students, employees of a specific firm or educationally/economically disadvantaged persons are vulnerable to coercion or undue influence. The checklists listed above for other populations should be used as a guide to ensure that you have provided sufficient information.*

N/A

17.0 Community-Based Participatory Research

17.1 Describe involvement of the community in the design and conduct of the research.

Response: N/A

Note: “Community-based Participatory Research” is a collaborative approach to research that equitably involves all partners in the research process and recognizes the unique strengths that each brings. Community-based Participatory Research begins with a research topic of importance to the community, has the aim of combining knowledge with action and achieving social change to improve health outcomes and eliminate health disparities.

18.0 Sharing of Results with Subjects

18.1 Describe whether or not results (study results or individual subject results, such as results of investigational diagnostic tests, genetic tests, or incidental findings) will be shared with subjects or others (e.g., the subject’s primary care physicians) and if so, describe how it will be shared.

Response: Sleep apnea and nighttime oxygenation results will be reported to participants and, if abnormal, to the participant’s primary provider if we receive permission from the participant to do so.

19.0 Setting

19.1 Describe the sites or locations where your research team will conduct the research.

Response: Roswell Park Cancer Institute, VA WNYHS and Cancer Care of Western New York will be the sites used to conduct the research.

19.2 Identify where your research team will identify and recruit potential subjects.

Response: The research team will identify and recruit potential subjects in the thoracic clinics at Roswell Park Cancer Institute, VA WNYHS and Western New York oncology offices and community centers that provide service to patients with lung cancer.

19.3 Identify where research procedures will be performed.

Response: Research procedures will be conducted in the thoracic clinics at Roswell Park Cancer Institute, VA WNYHS and Western New York oncology offices and community centers that provide service to patients with lung cancer.

19.4 Describe the composition and involvement of any community advisory board.

Response: N/A

19.5 For research conducted outside of the organization and its affiliates describe:

- Site-specific regulations or customs affecting the research for research outside the organization.
- Local scientific and ethical review structure outside the organization.

Response: N/A

20.0 Resources Available

20.1 Describe the qualifications (e.g., training, experience, oversight) of you and your staff as required to perform their role. When applicable describe their knowledge of the local study sites, culture, and society. Provide enough information to convince the IRB that you have qualified staff for the proposed research. Note- If you specify a person by name, a change to that person will require prior approval by the IRB. If you specify people by role (e.g., coordinator, research assistant, co-investigator, or pharmacist), a change to that person will not usually require prior approval by the IRB, provided that person meets the qualifications described to fulfill their roles.

Response: The PI completed a 2-year fellowship in Sleep and Respiratory Neurobiology at the University of Pennsylvania in 2006 and has conducted a variety of funded sleep studies at RPCI. The PI has collaborated with medical oncology for the past 5 years and thoracic surgery for the past year at RPCI and the VA WNYHS. The research team includes School of Nursing faculty who are sleep experts serving as co-investigators ([name] and [name]), a graduate nursing student learning to become a sleep scientist ([name]), two consultants ([name] and [name]) who are experts in insomnia treatment and light therapy to improve circadian rhythms and a collaborating thoracic surgeon ([name]). The PI has been looking for a project to collaborate with [name] at Cancer Care of Western New York.

Describe other resources available to conduct the research: For example, as appropriate:

20.2 Justify the feasibility of recruiting the required number of suitable subjects within the agreed recruitment period. For example, how many potential subjects do you have access to? What percentage of those potential subjects do you need to recruit?

Roswell Park Cancer Institute admits approximately 700 new patients with lung cancer annually. More than 400 of those 700 patients have stage I-III disease. Fifty lung cancer survivors with sleep continuity disturbance will

be recruited over 2 years. Not all lung cancer survivors have sleep continuity disturbance, but in our current sleep study, we were able to recruit 20 lung cancer survivors with insomnia within 6 months at Roswell Park Cancer Institute. Retention rate of study participants is anticipated to be 80% based on our previous experience. Oversampling will result in the desired target sample size at this rate. At the time of enrollment in the study, three forms of contact information will be obtained, email address, telephone number, and address for delivery of the data collection instruments and return mailers. In addition, an alternate contact person will be obtained to help decrease loss to follow up due to the length of the study.

20.3 Describe the time that you will devote to conducting and completing the research.

Response: 20% of the PI's research time, 10% of the Co-I's time and the RA will work 10 hours/week on this study.

20.4 Describe your facilities.

Response: Recruitment Site: Roswell Park Cancer Institute (RPCI) was founded in 1898 is America's first cancer center and holds the National Cancer Institute designation of "comprehensive cancer center." RPCI has 133 hospital beds and 12 multidisciplinary clinics and is the only comprehensive cancer center of Western New York area. As a member of the prestigious National Comprehensive Cancer Network, RPCI has played a vital part in setting clinical guidelines for the care of Oncology patients. RPCI plays a pivotal part in cancer research with several ongoing funded research projects.

The thoracic clinic provides state of the art comprehensive multidisciplinary care to approximately 700 patients with lung cancer annually. The presence of several specialties -pulmonary medicine, medical oncology and thoracic surgery along with the undiagnosed clinic in a single location with additional support from nearby radiation oncology clinics and interventional radiation ensures excellent patient care and satisfaction. The patients with lung masses and suspected lung cancer are promptly seen by the pulmonary clinic or the undiagnosed clinic and scheduled for diagnostic biopsy procedures. Several multidisciplinary meetings are conducted each week to make complicated management decisions for the patients.

The VA WNYHS provides care to approximately 100 newly diagnosed veterans with lung cancer annually.

Research Offices: The University at Buffalo School of Nursing (SON) is located in Wende Hall, a newly renovated historic building on the South Campus, is in close proximity to the four other Health Sciences Schools of Medicine, Dentistry, Pharmacy, and Public Health and Health Related

Professions. As a SON situated in a research intensive university, creation, translation, and transmission of knowledge is an expectation of faculty in support of the University mission. Excellence in teaching and service to the university, the community and the profession are also expectations in support of the mission and goals of the University and SON. A variety of offices, classrooms, and conference rooms are available for faculty. There are two videoconferencing rooms in the SON to accommodate a recently funded distance education PhD grant as well as other videoconferencing facilities located in the Health Sciences Library. The PI has 10 wrist-actigraphs (Octogonal Sleep Watch 2.0) and ActionW software (Version 2.0) purchased from Ambulatory Monitoring, Ardsley, NY, to use in this study.

20.5 Describe the availability of medical or psychological resources that subjects might need as a result of an anticipated consequences of the human research.

Response: Roswell Park Cancer Institute, VA WNYHS and Western New York oncology offices and community centers that provide service to patients with lung cancer have dedicated social workers and a psychologist assigned to ambulatory clinics.

20.6 Describe your process to ensure that all persons assisting with the research are adequately informed about the protocol, the research procedures, and their duties and functions.

Response: When we begin a new study, we take turns reading the research protocol out loud during a team meeting to ensure each member of the team has read the protocol and understands it. Team members are encouraged to ask questions about the research protocol during the meeting. We each perform the research procedures that we ask research participants to engage in to increase our understanding of the procedures/process and ensure the data collection instruments collect the information that we require.

21.0 Prior Approvals

21.1 Describe any approvals that will be obtained prior to commencing the research. (E.g., school, external site, funding agency, laboratory, radiation safety, or biosafety approval.)

Response: This study is funded by the Oncology Nursing Society Foundation. Before releasing the funding, University @ Buffalo's IRB approval is needed.

22.0 Recruitment Methods

22.1 Describe when, where, and how potential subjects will be recruited.

The Principal Investigator will screen medical records for eligibility criteria. Potential participants will be approached face to face and after

signed informed consent will be randomly assigned to control and experimental group.

22.2 Describe the source of subjects.

Response: All participants at Roswell Park Cancer Institute, VA WNYHS and Western New York oncology offices and community centers that provide service to patients with lung cancer meeting the eligibility criteria.

22.3 Describe the methods that will be used to identify potential subjects.

Potential participants will be screened for eligibility criteria by reviewing electronic medical records for eligibility in the thoracic clinics at Roswell Park Cancer Institute, VA WNYHS and Western New York oncology offices and community centers that provide service to patients with lung cancer.

22.4 Describe materials that will be used to recruit subjects. (Attach copies of these documents with the application. For advertisements, attach the final copy of printed advertisements. When advertisements are taped for broadcast, attach the final audio/video tape. You may submit the wording of the advertisement prior to taping to preclude re-taping because of inappropriate wording, provided the IRB reviews the final audio/video tape.)

Response: An IRB-approved recruitment flyer will be used.

22.5 Describe the amount and timing of any payments to subjects.

Response: A total of \$50 will be paid to participants that complete data collection. After completing baseline data participants will receive \$25 and after completing f/u data collection participants will receive another \$25.

23.0 Local Number of Subjects

23.1 Indicate the total number of subjects to be accrued locally.

Response: 50

23.2 If applicable, distinguish between the number of subjects who are expected to be enrolled and screened, and the number of subjects needed to complete the research procedures (i.e., numbers of subjects excluding screen failures.)

Response: 50 recruited and 40 to complete. We anticipate approximately 80% retention from previous research on this patient population.

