3.0 Inclusion and Exclusion Criteria

3.1 Describe the criteria that define who will be included or excluded in your final study sample.

Fifty-two lung cancer survivors with sleep continuity disturbance will be recruited over 2 years. Eligibility criteria include the following: age >21 , stage I-III, non-small cell lung cancer, ≥ 6 weeks and ≤ 3 years post-surgical resection who are medically and psychiatrically stable. Subjects must be able to give consent. An NCI-designated comprehensive cancer center with a well-established thoracic surgery practice will be the recruitment site. A collaborative recruitment arrangement in the past has resulted in successful recruitment goal achievement.

3.2 Describe how individuals will be screened for eligibility.

The PI or research assistant (RA) will screen all eligible participants for sleep apnea using the ApneaLink device. Participants who screen positive for sleep apnea will receive 2 printed reports of the ApneaLink results: one for themselves and a copy for their provider, who will be advised to refer the participant for further sleep evaluation. Following a negative screen for sleep apnea, participants will be evaluated for sleep continuity disturbance through the use of Insomnia Severity Index, Epworth Sleepiness Scale and 14-day sleep diaries. Participants will also be screened for circadian activity rhythm disturbance with 14-day actigraphy and Morningness-Eveningness Questionnaire. A folder will be provided with each of the pretreatment instruments to complete and an actigraph to wear 24/7 at home. Following completion of pretreatment measures, participants will be randomized using a random number assignment to either red-yellow (control dim light) versus blue-green (experimental bright light) directed light therapy. Participants will be trained on how to wear the directed light therapy for 60-minutes within 30-minutes upon awakening for 1-week (Redd et al., 2014).

3.3 *Indicate specifically whether you will include or exclude each of the following special populations: (You may not include members of these populations as subjects in your research unless you indicate this in your inclusion criteria.)*

- *Adults unable to consent*
- *Individuals who are not yet adults (infants, children, teenagers)*
- *Pregnant women*
- *Prisoners*

These populations will not be included in the study.

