9.0 Procedures Involved

9.1 *Describe and explain the study design.*

This pilot study will include 52 lung cancer survivors using a 2X2 mixed model with Pre-Post assessments in two groups. Twenty-six participants will be randomized to red yellow directed light (control) and 26 participants will receive blue green (experimental) directed light therapy. The light source (Re-Timer) will be worn for 60-minutes every morning within 30-minutes upon awakening for 1-week. Participants will receive a weekly telephone call to ensure adherence to treatment plan and screen for safety/adverse events.

9.2 *Provide a description of all research procedures being performed and when they are performed, including procedures being performed to monitor subjects for safety or minimize risks.*

Screening for inclusion criteria includes a YES response to the following questions:

Are at least 21 years of age?

Do you have a diagnosis of non-small cell lung cancer stage I, II or III?

Have you had your lung cancer surgically removed at least 6 weeks ago, but not longer than 3 years ago?

Screening for exclusion criteria includes a NO response to the following questions:

Do you have any unmanaged medical or psychiatric diagnoses?

Are you currently pregnant?

Do you have a diagnosis of epilepsy?

Following informed consent, in order to rule-out sleep apnea as a confounder and assess for respiratory disturbance, all eligible participants will be screened for sleep apnea and hypoxia using the portable ApneaLink device for one night. Following a negative screen for sleep apnea, demographics, diagnoses, treatments, comorbidities, etc. will be recorded using the Demographics and Treatment Survey. Fatigue will be measured using the Functional Assessment of Chronic Illness Therapy Fatigue (FACIT) (Cella, Lai et al. 2011). Sleep continuity disturbance will be determined by Insomnia Severity Index (Bastien et al., 2001), 14-day sleep diary and the Epworth Sleepiness Scale (Johns 1991). Circadian activity rhythm disturbance will be assessed using the 14-day actigraph (Ambulatory Monitoring, Inc, Ardsley, NY) and Morningness-Eveningness Horne-Ostberg/Questionnaire (MEQ) (Horne and Ostberg 1976). Surveys and actigraphy will be performed at baseline and again after treatment ends. Expectation for treatment effectiveness will be assessed with the investigator developed Expectation Questionnaire before and

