11.0 Data Management

11.1 Describe the data analysis plan, including any statistical procedures.

Hypothesis testing will be conducted using 2x2 ANOVAs for the first specific aim, with Logistic Regressions for the second specific aim (predicting treatment response and non-response) and with Linear and Logistic Regressions for the third specific aim (predicting illness severity and treatment response).

11.2 Provide a power analysis.

Response:

The primary outcome for sleep is the sleep efficiency score. Previous research has indicated that persons with satisfactory sleep have a sleep efficiency score exceeding 85, whereas persons reporting unsatisfactory sleep have a score at most 70, with both groups reporting a standard deviation of approximately 15. The estimated effect size from this study

is 1. The goal of this study is to improve sleep efficiency from an unsatisfactory level to a satisfactory level. Using a large effect size of .08 with a one-tailed significance of .025 and power of 80%, the required sample size for the two-group comparison is 26 per group for a total sample of 52.

11.3 Describe the steps that will be taken to secure the data (e.g., training, authorization of access, password protection, encryption, physical controls, certificates of confidentiality, and separation of identifiers and data) during storage, use, and transmission.

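### Section 11.2 needs 52 analysed participants for 80% power, but the plan recruits 50 or 52 and expects 40 to complete, which gives about 69% power at d = 0.8

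*Combined protocol and SAP*

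**What the plan says.** Section 11.2 names sleep efficiency as the primary sleep outcome. It contrasts a satisfactory score above 85 with an unsatisfactory score of at most 70, gives an SD of about 15, and reports an effect size of 1 from this. The calculation then uses a different value: "Using a large effect size of .08 with a one-tailed significance of .025 and power of 80" per cent. Its result is that "the required sample size for the two-group comparison is 26 per group for a total sample of 52". Dropout is not mentioned.

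The enrolment numbers elsewhere are:

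- Section 3.1: "Fifty-two lung cancer survivors with sleep continuity disturbance will be recruited over 2 years".
- Section 9.1: "This pilot study will include 52 lung cancer survivors using a 2X2 mixed model with Pre-Post assessments in two groups", with 26 in each arm.
- Section 20.2: "Fifty lung cancer survivors with sleep continuity disturbance will" be recruited over 2 years, at an anticipated 80% retention, followed by "Oversampling will result in the desired target sample size at this rate".
- Section 23.1: 50.
- Section 23.2: "50 recruited and 40 to complete. We anticipate approximately 80% retention from previous research on this patient population".

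**The concern.** The 52 in section 11.2 is the number that must contribute data if the comparison is to have 80% power. Sections 3.1 and 9.1 use the same 52 as the number recruited and randomised, so any loss takes the trial below its own requirement. Sections 20.2 and 23 start from 50 and forecast 40 completers, 12 short of 52 (23%). The only text that addresses the gap is the oversampling sentence, and no number supports it.

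Two things are at stake. A null result would be read against a claimed 80% power that the plan's own retention forecast does not deliver. And a reader cannot tell whether 50 or 52 are to be enrolled, or what size of effect the trial can detect.

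**Working it through.** **Inputs.** One-tailed alpha .025, power 80%, effect size printed as .08, SD 15 and an alternative effect size of 1 (all section 11.2); 1:1 allocation (section 9.1); 80% retention (sections 20.2 and 23.2); 50 or 52 enrolled and 40 completing (sections 3.1, 9.1, 20.2, 23.1, 23.2).

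**Formula.** Two-sample t test with n per group: df = 2n − 2, noncentrality = d × √(n/2), and power = P(T > t at .975 with df), where T is noncentral t.

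**Step 1: reproduce the plan's figure.**

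- d = 0.8 needs n = 25.5, rounded up to 26 per group, or 52. This matches section 11.2. At n = 26, noncentrality is 0.8 × √13 = 2.884, the critical value is 2.009 and power is 80.7%.
- d = .08 as printed needs about 2,454 per group.
- d = 1 needs 17 per group.

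So the calculation used 0.8, and 52 is an analysed number with no margin for attrition.

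**Step 2: expected completers.** 50 × 0.80 = 40, or 20 per group. 52 × 0.80 = 41.6, or about 41 to 42. Having 52 completers at 80% retention would take 52/0.80 = 65 recruited, and no section gives a number above 52.

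**Step 3: power and detectable effect.** For n = 20, noncentrality is 0.8 × √10 = 2.530, the critical value is 2.024 and power is 69.3%.

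| Analysed per group | Power, d = 0.8 | Power, d = 1 | d detectable at 80% power | Points at SD 15 |
|---|---|---|---|---|
| 26 / 26 | 80.7% | 94.2% | 0.79 | 11.9 |
| 25 / 25 | 79.1% | 93.4% | 0.81 | 12.1 |
| 21 / 21 | 71.6% | 88.5% | 0.89 | 13.3 |
| 21 / 20 | 70.4% | 87.7% | 0.90 | 13.5 |
| 20 / 20 | 69.3% | 86.9% | 0.91 | 13.6 |

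Even 50 enrolled with no loss at all falls just under 80% at d = 0.8.

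**Step 4: the planned 2×2 pre-post ANOVA (section 11.1).** Its group-by-time interaction is equivalent to a t test on change scores. With equal SDs, no baseline difference and 0.8 as the post-treatment difference, the effect becomes 0.8/√(2(1 − ρ)), where ρ is the pre-post correlation. The plan gives no ρ, so these values are assumed:

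| Assumed ρ | Change-score effect | 20 per group | 26 per group |
|---|---|---|---|
| 0.4 | 0.73 | 61% | 73% |
| 0.5 | 0.80 | 69% | 81% |
| 0.6 | 0.89 | 79% | 89% |
| 0.7 | 1.03 | 89% | 95% |

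The fall from 26 to 20 per group costs about 7 to 12 percentage points over this range.

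**The case against.** The best reply is that 69% holds only at d = 0.8. Section 11.2 also derives an effect of 1 and says the aim is to move sleep efficiency from unsatisfactory to satisfactory. At d = 1, 40 completers give 86.9%. That figure is right and belongs beside the 69%. But the 80% claim and the 52 come from 0.8; sizing on 1 would have produced 17 per group.

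Second, the planned analysis is the 2×2 ANOVA, whose interaction reaches 80% power with 20 per group once ρ is about 0.61 or more. This also stands: whether the ANOVA itself falls below 80% cannot be settled from the documents. The finding is therefore limited to the two-group comparison that section 11.2 actually powers.

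Third, sections 20.2 and 23 agree with each other if the target is 40, since 40/0.80 = 50. On that reading the oversampling sentence is sound, and the error is two unreconciled targets. This is plausible, but the only sample-size target the plan justifies is 52, and against 52 the sentence cannot be true.

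Fourth, section 13.3 keeps collecting data from participants who stop wearing the device, so the number analysed could exceed the number completing treatment. No missing-data rule is stated, though, and 40 is the only completer number given.

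Finally, this is a pilot. It nevertheless makes a formal power claim and plans hypothesis tests, so the claim should match its numbers.

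**Conclusion.** The concern holds and must be fixed. The plan's own completer number does not deliver the 80% power stated in section 11.2. For the two-group comparison at d = 0.8 and one-tailed .025, 40 completers give 69.3%. If 52 are enrolled, the 41 to 42 expected completers give 70.4% to 71.6%. Separately, the enrolment number is contradictory (50 or 52) and the printed effect size is wrong by a factor of ten.

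The power figures rest on reading .08 as 0.8, equal arms (except the 21/20 split), and an analysis of completers only. They do not apply at d = 1, where power stays above 80%, and they say nothing definite about the 2×2 interaction without a pre-post correlation.

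**What to change.** - Choose one enrolment number and one completer number, and use them in sections 3.1, 9.1, 11.2, 20.2, 23.1 and 23.2.
- Correct .08 to 0.8 in section 11.2.
- If 50 enrolled and 40 completing stands, restate section 11.2 along these lines: *With 40 completers (20 per group), a two-group comparison at one-tailed .025 has about 69% power at d = 0.8, and 80% power for d of about 0.91 (13.6 sleep-efficiency points at SD 15).*
- If 52 enrolled stands, the matching statement is about 42 completers, 71% to 72% power at d = 0.8, and 80% power for d of about 0.89 (about 13.3 points).
- Delete the oversampling sentence in section 20.2. It could stay only if section 11.2 is rewritten around a target of 40 completers.
- If power is to be claimed for the 2×2 ANOVA, state the pre-post correlation assumed.

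The cost is wording only, with no added participants. The stated power at d = 0.8 drops from 80% to about 69% (or 71% to 72% with 52 enrolled).

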7.0 Study Timelines

7.1 *Describe the duration of an individual subject's participation in the study.*

Subjects will be expected to participate for approximately 10 weeks during which ApneaLink screening, completion of pre-intervention data collection, 1 week for intervention, and completion of post-intervention data collection will occur.

7.2 *Describe the duration anticipated to enroll all study subjects.*

Approximately 18 months.

7.3 *Describe the estimated date for the investigators to complete this study (complete primary analyses)*

December, 2017.

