28.0 Consent Process

28.1 Indicate whether you will be obtaining consent

Written informed consent will be obtained at the recruitment.

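### Section 23 plans 50 recruited and 40 completing, below the 52 randomised that 9.1 and 11.2 require, and states no allowance for people removed by the apnea screen after consent

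*Combined protocol and SAP*

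**What the plan says.** All references are to the combined protocol and SAP.

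- **Counts.** Section 23.1 gives 50 as the number to be accrued. Section 23.2 asks for those screened and enrolled to be distinguished from those needed to complete, leaving out screen failures. The answer is "50 recruited and 40 to complete. We anticipate approximately 80% retention from previous research on this patient population". Section 20.2 also says fifty, whereas 3.1 says fifty-two.
- **Design and power.** Section 9.1 randomises 26 to each arm. Section 11.2 derives 26 per group, 52 in total, from a one-tailed 0.025 test with 80% power. It prints the effect size as .08 and, just before that, gives an estimate of 1.
- **Retention.** Section 20.2: "Retention rate of study participants is anticipated to be 80% based on our previous experience", followed by "Oversampling will result in the desired target sample size at this rate". No oversampled number is given.
- **Order of events.** Section 28.1: "Written informed consent will be obtained at the recruitment". Section 9.2: "Following informed consent, in order to rule-out sleep apnea as a confounder and assess for respiratory disturbance, all eligible participants will be screened". Under 3.2, only those with a negative apnea screen go on to the evaluation of sleep continuity disturbance and circadian rhythm, and randomisation follows those pretreatment measures. Section 22.1 describes random assignment after signed consent and mentions no screen in between.
- **Duration.** Section 7.2 gives the enrolment period as "Approximately 18 months". Sections 3.1 and 20.2 say two years.

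**The concern.** Two things do not fit. First, the accrual figure is smaller than the number the design has to randomise, and the completer figure is smaller again, while 11.2 still claims 80% power. Second, consent comes before a screen that removes people, and 23.2 goes from recruited to completing through retention alone, although the prompt asks about screen failures.

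At stake is whether the trial delivers the power it states, and whether anyone can tell when accrual is finished. A team that stops at 50, one that stops at 52, one that counts consents and one that counts people past the screen would each be following some sentence of the plan, and they would end with different numbers randomised.

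**Working it through.** **Inputs.** 50 recruited, 40 completing, 80% retention (23.2, 20.2); 26 per arm, one-sided 0.025, 80% power (9.1, 11.2). The apnea-positive share *s* is not in the documents and is assumed over 0 to 40%.

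**1. Reproduce the plan's figures.**
- Completers: 50 × 0.80 = 40, exactly as stated.
- Sample size, two-sample t test, one-sided 0.025, power 80%: a standardised difference d = 0.8 needs 25.5, so 26 per arm and 52 in total, as stated. The printed .08 would need 2,454 per arm and d = 1 would need 17. Only 0.8 matches, so 0.8 is used below; that is a reading of the printed value.

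**2. Compare accrual with the design, with no screen failures at all.**
- 50 < 52, so 26 + 26 cannot be randomised from 50.
- Power at d = 0.8: 80.7% with 26 per arm and 69.3% with 20 per arm. The gap is 80.7 − 69.3 = 11.4 points.
- If 52 are randomised and 80% retained, 52 × 0.80 = 41.6 complete, about 21 per arm, with power 71.6%. Keeping 52 completers would take 52 / 0.80 = 65 randomised. The 52 in 11.2 therefore contains no dropout allowance.

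**3. Add the apnea screen, on one reading.** Suppose the 50 are consents and the 80% applies after the screen. Then randomised = 50 × (1 − *s*) and completers = 0.80 × 50 × (1 − *s*). Power is for d = 0.8, one-sided 0.025, with completers split equally.

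| Assumed *s* | Randomised | Completers | Power | Consents for 52 randomised, 52/(1 − *s*) |
|---|---|---|---|---|
| 0% | 50 | 40 | 69.3% | 52 |
| 10% | 45 | 36 | 64.5% | 58 |
| 20% | 40 | 32 | 59.1% | 65 |
| 30% | 35 | 28 | 53.1% | 75 |
| 40% | 30 | 24 | 46.6% | 87 |

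The 0% row is the reference. The fall from 80.7% to 69.3% is there before the screen removes anyone; a 10% share takes off a further 69.3 − 64.5 = 4.8 points.

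**4. The other two readings.**
- If the 80% covers all loss from consent, 40 complete by definition. At *s* = 10% this needs 40/45 = 89% retention after randomisation, and at *s* = 20% it needs 40/40 = 100%.
- If the 50 are counted after the screen, 50 are randomised and 40 complete, but the number to consent is 50/(1 − *s*), for example 56 at 10% and 63 at 20%. The plan states no such number.

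On both of these readings power at the stated 40 completers is still 69.3%.

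**The case against.** The strongest reply is that the counts are loosely worded, not wrong. The multiplication is exact. Sections 3.1 and 20.2 describe the people recruited as having sleep continuity disturbance, which 3.2 evaluates only after a negative apnea screen, so *recruited* may already mean past the screen. The start of the 80% is undefined and could be consent. Section 20.2 promises oversampling, and 12.1 has weekly accrual reviews with the statistician alerted if accrual or retention falls below what is needed. Nothing says that accrual closes at 50 consents.

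Much of this stands. A reader might infer that the apnea screen is why 26 per arm is out of reach, or that 40 completers cannot be reached. The documents support neither: 26 per arm fails because 50 < 52 whatever the screen does, and 40 survives on either alternative reading. A reader might also project accrual from the report in 20.2 that "we were able to recruit 20 lung cancer survivors with insomnia within 6 months". That was a different study at one centre, its counting point is not given, and this trial also recruits at other locations (19.2), so no limit on screen failures can be drawn from it.

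The effect size matters too. At d = 1, the other value in 11.2, 20 per arm gives 86.9% power, and 18/16/14/12 per arm give 83/78/72/65%. But 11.2 does not size the trial on 1.

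The reply does not remove the conflict. The oversampling sentence carries no number and is tied to retention. The weekly review needs a target to compare against, and the plan offers 50, 52 and 40.

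**Conclusion.** The point holds as an inconsistency in the planned counts, together with an allowance that is not stated. Without any outside assumption, the accrual of 50 is below the 52 to be randomised, and the expected 40 completers give about 69% power, not 80%. This rests on d = 0.8 as the intended effect size, on the two-group comparison used in 11.2, and on only completers contributing to the pre-post analysis.

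The apnea screen can deepen the shortfall, to between about 65% and 47% power for shares of 10 to 40%. That applies only if the 50 are consents and the 80% starts after the screen, and the share itself is assumed. The plan does not settle either condition, and that is part of the defect. The evaluation of sleep continuity disturbance before randomisation may remove further people, and no allowance is stated for that either. The conflict between 18 months and two years stands independently of these assumptions.

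**What to change.** - In 3.1, 9.1, 20.2 and 23.1–23.2, reconcile 50 with 52. Define the target as patients randomised after the apnea screen and the pretreatment evaluation, and bring 22.1 into line with that order.
- In 23.2, give three counts: consented, randomised and completing. State the assumed screen-failure share and say that the 80% retention runs from randomisation, or from whichever point is meant.
- In 11.2, state the power at the expected number of completers and correct or explain the printed effect size.
- Use one recruitment duration in 3.1, 7.2 and 20.2.

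The cost is amendment wording. The stated power becomes less favourable: about 69% at 40 completers, or about 72% at 21 per arm if 52 are randomised. No extra enrolment is needed if the figures are simply restated. If the sponsor prefers to hold 52 randomised, the cost is more consents and one-night screens, for example 58 consents at an assumed 10% share or 65 at 20%.
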